### 3.1.3 Definition of Baseline

For all variables except lipids and liver enzymes variables, pre-dose measurements on Baseline visit (Day 1) will be considered the baseline values. If the measurement at this visit is not available, the last measurement prior to the first dose of study drug may be used as the baseline value unless it is stated otherwise. The scheduled baseline visit for FibroScan, liver biopsy, DXA scan, and ELF™ is Screening. Baseline lipid variables including Total Cholesterol, HDL-C, LDL-C, Triglycerides, non-HDL cholesterol will be the average of Screening and Baseline visit (Day 1) values. Baseline liver enzymes variables including ALT and AST will be the average of Pre-Baseline and Baseline visit (Day 1) values. If one is missing for lipids and liver enzymes variables, the available one will be used.

### 3.1.4 Summary Statistics

Categorical data will generally be summarized with counts and percentages of subjects. The denominator used for the percentage calculation will be clearly defined. Continuous data will generally be summarized with descriptive statistics including n (number of non-missing values), mean, median, standard deviation, minimum, and maximum. For certain continuous data, it will be summarized with descriptive statistics including n (number of non-missing values), arithmetic mean, arithmetic standard deviation, geometric mean, geometric coefficient of variation, median, minimum, and maximum. PK concentrations will be summarized with the set of continuous parameters including geometric mean and will add the statistic of number of samples below the limit of quantification (nblq).

All individual subject data will be listed as measured.

### 3.1.5 Hypothesis Testing

The statistical hypotheses will be tested at the 2-sided, 0.05 significance for the parameters with neutral direction unless specified otherwise.

### 3.1.6 Handling of Dropouts and Missing Data

Missing data can have an impact on the interpretation of the trial data. In general, values for missing data will not be imputed.

Where appropriate, safety data for subjects that did not complete the study will be included in summary statistics. For example, if a subject received study drug, the subject will be included in a summary of AEs according to the treatment received; otherwise, if the subject is not dosed then they will be excluded from the summary. If safety laboratory results for a subject are missing for any reason at a time point, the subject will be excluded from the calculation of summary statistics for that time point. If the subject is missing a pre-dose value, then the subject will be excluded from the calculation of summary statistics for the pre-dose value and the change from pre-dose values.

Values for missing safety laboratory data will not be imputed; however, a missing baseline result will be replaced with a screening result, if available. If no pre-treatment laboratory value is available, the baseline value will be assumed to be normal (i.e., no grade [Grade 0]) for the summary of graded laboratory abnormalities.

Values for missing vital signs data will not be imputed; however, a missing baseline result will be replaced with a screening result, if available.

Below limit of quantification (BLQ) PK concentration at pre-dose at Baseline will be imputed as zero and the other pre-dose BLQ PK concentrations will be imputed as half of the low limit of quantification (0.5\*LLOQ).

# 3.2 Analysis Populations

### 3.2.1 Full Analysis Set (FAS)

The FAS will include all subjects who were randomized into the study. The FAS will be the primary analysis set for efficacy analyses.

Subjects who receive a dose of study drug other than that to which they were randomized for the entire duration of treatment will be analyzed according to treatment group to which they were randomized.

### 3.2.2 Safety Set

The Safety Set will include all subjects who received at least one dose of study drug. The Safety Set will be the primary analysis set for safety analyses.

Subjects who received a dose of study drug other than that to which they were randomized for the entire duration of treatment will be analyzed according to the dose of study drug received. All data collected during treatment plus 30 days after last dose of study drug will be included in the safety summaries.

### 3.2.3 F4 Safety Set

The F4 Safety Set will be a subset of the Safety Set. It will exclude Safety Set subjects who are not confirmed F4 fibrosis by histology central reads.

### 3.2.4 PK Analysis Set

The PK Analysis Set will include all randomized subjects who took at least one dose of study drug and for whom concentration data of EFX is available.

### 3.2.5 Biomarker Analysis Set

The Biomarker Analysis Set will include data from subjects in the Safety Set who have the baseline and at least one on-study measurement to provide interpretable results for ELF™ Test score or pro-C3 levels.

### 3.2.6 Per Protocol Analysis Set (PPAS)

The PPAS is defined as any subject who is randomized, receives at least one dose of study drug without any major protocol deviations. A full detail of inclusions and exclusions from PPAS will be in the classifications specifications and finalized before unblinding.

### 3.2.7 Liver Stiffness Evaluable Analysis Set

The Liver Stiffness Evaluable Analysis Set will be a subset of the FAS. It will include all FAS subjects who have Baseline and Week 16 liver stiffness as evaluated by FibroScan.

### 3.2.8 Liver Biopsy Evaluable Analysis Set

Liver Biopsy Evaluable Analysis Set will be a subset of the FAS. It will include all FAS subjects with confirmed F4 fibrosis at baseline by central reads who have Baseline and Week 16 liver biopsy results. It will be the analysis population for the responders based on histologic evaluation of NAS system and fibrosis stage.

### 3.2.9 Stratification

Not Applicable.

## 3.3 Subject Data and Study Conduct

### 3.3.1 Subject Disposition

Counts and percentages of subjects who were screened (signed informed consent), discontinued early during screening (screen failures), and randomized will be summarized in total based on all screened subjects. Reasons for early discontinuation will also be summarized. In addition, discontinuation contributed by COVID-19 will be summarized.

Counts and percentages of subjects in each of the following disposition categories will be presented by treatment and in total based on all randomized subjects:

- Subjects who were randomized
- Subjects who started study drug
- Subjects who completed the treatment
- Subjects who withdrew from the treatment
- Subjects who completed the study
- Subjects who withdrew from the study

For randomized subjects who withdraw from the treatment and withdraw from the study, the primary reason for the withdrawal will be summarized. In addition, early discontinuation from the treatment contributed by COVID-19 and early discontinuation from the study contributed by COVID-19 will be summarized.

#### 3.3.2 Protocol Deviations

Protocol deviations will be defined in the Protocol Deviation Plan. Counts and percentages of subjects with CSR reportable protocol deviations by deviation category will be summarized by treatment and in total based on all randomized subjects. All protocol deviations and COVID-19 related protocol deviations will be listed.

### 3.3.3 Analysis Populations

Counts and percentages of subjects in each analysis population will be summarized by treatment and in total based on all randomized subjects.

### 3.3.4 Demographic and Baseline Characteristics

The following demographic and baseline characteristics will be summarized:

- Age (years) and age categories (<45 years, ≥45 to <65 years, ≥65 years)

- Sex
- Race
- Ethnicity
- Height (cm) at Screening
- · Weight (kg) at Baseline
- Body mass index (BMI) (kg/m²) at Baseline and BMI categories at Baseline (<30 kg/m², ≥30 kg/m²)
- Waist circumference (cm) at Baseline
- Hip circumference (cm) at Baseline

- Waist-to-hip ratio at Baseline
- · Type 2 diabetes status at Screening
- Statin Use at Baseline
- Vitamin E/Thiazolidinedione Use at Baseline
- Fibrosis stage (local read) at Screening
- Biopsy diagnosis (local read) at Screening
- NAS and NAS components (local read) at Screening
- Fibrosis stage (central read) at Screening
- Biopsy diagnosis (central read) at Screening
- NAS and NAS components (central read) at Screening
- Liver Stiffness as Evaluated by FibroScan at Screening (kiloPascals [kPa])
- Liver Steatosis as Evaluated by FibroScan at Screening (Controlled Attenuation Parameter [CAP])
- Alanine aminotransferase (U/L) and Aspartate Aminotransferase (U/L) at Baseline
- Triglyceride (mg/dL), Total Cholesterol (mg/dL), LDL-C (mg/dL), HDL-C (mg/dL), and non-HDL-C (mg/dL) at Baseline
- Hemoglobin A1c (%) at Baseline
- Endogenous FGF21 at Baseline
- MELD Score at Baseline
- CP Score at Baseline
- ELF Score at Baseline
- Pro-C3 (ug/L) at Baseline
- ALT >= 3xULN at Baseline
- AST >= 3xULN at Baseline

Demographic and baseline characteristics will be summarized with descriptive statistics or counts and percentages of subjects as appropriate by treatment and in total for all randomized subjects and each defined analysis population if the analysis population composition is different than all randomized subjects.

### 3.3.5 Medical History

Medical history will be coded to system organ class (SOC) and preferred term using the Medical Dictionary for Regulatory Activities (MedDRA) version 22.0. Counts and percentages of subjects with medical history by SOC and preferred term will be summarized by treatment and in total based on all randomized subjects.

#### 3.3.6 Concomitant Medications

Concomitant medications will be coded to anatomical therapeutic chemical (ATC) class and preferred term using the World Health Organization (WHO) Drug Dictionary version 2019G B3. For summary purposes, medications will be considered prior medications if they stopped prior to the first dose of study drug and concomitant medications if they were taken at any time on or after the first dose of study drug (i.e. started prior to the first dose of study drug and were ongoing or started after the first dose of study drug).

Counts and percentages of subjects taking concomitant medications by ATC class and preferred term will be summarized by treatment and in total based on the Safety Set. The use of any prior medication or concomitant medication will be listed for all randomized subjects.

### 3.3.7 Study Drug Exposure and Compliance

Weeks of exposure to study drug will be calculated as:

(date of last dose of study drug - date of first dose of study drug + 1) / 7

Weeks of exposure to study drug will be summarized by treatment based on the Safety Set with descriptive statistics and with counts and percentages of subjects with exposure in the following categories:

- >0 to ≤4 weeks
- >4 to ≤8 weeks
- >8 to ≤12 weeks
- >12 to ≤16 weeks
- >16 weeks

The total number of injections administered will be calculated for each subject. A contingency table will be provided to display the number and percentage of subjects in each treatment group with the following number of injections: 1-3, 4-6, 7-9, 10-12, 13-15, >=16.

Subjects that miss 2 or more doses of study drug over the course of study participation are considered noncompliant. The frequency and percentage of subjects who are compliant and noncompliant will be summarized by treatment group.

### 3.4 Efficacy Assessment

Efficacy data will be summarized and analyzed by randomized treatment based on the FAS unless otherwise specified. For the secondary endpoints, the boxplots over time will be provided.

- 3.4.1 Secondary Efficacy Endpoints
- 3.4.1.1 Change from baseline in liver stiffness as evaluated by FibroScan® at Week 16

Liver stiffness will be assessed using FibroScan® at Screening and Week 16. Summary statistics at all visits for the values, change from baseline and percent change from baseline will be provided.

The change and percent change from baseline at Week 16 in liver stiffness expressed in kPa will be analyzed with an analysis of covariance (ANCOVA) model with treatment group as a factor and baseline liver stiffness as evaluated by FibroScan® as a covariate using the FAS. The treatment effect estimate, 95% CI and pvalues will be provided. Missing values at Week 16 will be imputed using the last-observed-carried-forward (LOCF) method. The same analysis will be repeated on the Liver Stiffness Evaluable Analysis Set and the PPAS, and no imputation will be performed.

The SAS sample code is listed:

```
proc glm;
  class TREATMENT;
  model CHG = TREATMENT BASE / p;
  lsmeans TREATMENT / stderr pdiff cl;
  estimate "EFX 50 mg : Placebo" TREATMENT -1 1;
run:
```

The Shapiro-Wilk normality test will be performed for the residuals from the model above. If the p-value is < 0.01, then non-parametric analyses will be explored.

3.4.1.2 Changes from baseline in non-invasive biomarkers including Pro-C3 at Weeks 12, 16 and 20, and liver fibrosis by ELF™ Test score at Weeks 6, 12 and 16

ELF™ Test score and its components including hyaluronic acid (HA), procollagen III amino terminal peptide (PIIINP), tissue inhibitor of metalloproteinase 1 (TIMP-1) will be measured at Screening, Week 6 and Week 16. Values and changes from baseline in ELF™ Test score and its components will be summarized descriptively. ANCOVA model with treatment group as a factor and baseline value as a covariate based on the FAS will be used for analyzing the change from baseline to Week 16. LS means, 95% confidence intervals and p-values will be presented. Missing values will be imputed using the LOCF method. The same analysis will be repeated on the Biomarker Analysis Set and the PPAS, and no imputation will be performed. The Shapiro-Wilk normality test will be performed for the residuals from the model above. If the p-value is < 0.01, then non-parametric analyses will be explored. Week 12 of ELF Test score and its components will be included in the summary and the change from baseline to Week 12 will be analyzed using the same ANCOVA model if the data is available.

Pro-C3 will be measured at Screening, Baseline (Day 1), Week 1, Week 4, Week 8, Week 12, Week 16 and Week 20 Safety follow-up. Values and changes from baseline in Pro-C3 will be summarized descriptively. The change and percent change from baseline to Weeks, 4, 8, 12, 16 and 20 will be analyzed using ANCOVA model in a manner similar to the ELF™ Test score and its components.

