5.2.2. Dosage and Administration

Detailed information regarding the preparation and administration of EFX or Placebo for this study is contained in the EFX Pharmacy Manual. Investigational medicinal product will be administered by subcutaneous injection once weekly as follows:

Main Study:

- Placebo QW for 16 weeks (n = 20)
- 28 mg EFX QW for 16 weeks (n = 20)
- 50 mg EFX QW for 16 weeks (n = 20)
- 70 mg EFX QW for 16 weeks (n = 20)

Cohort C:

- Placebo QW for 16 weeks (n = 10)
- 50 mg EFX QW for 16 weeks (n = 20)

The IMP will be administered by a weekly 1.0 mL subcutaneous injection into the abdomen at the clinic by a qualified staff member. The date and time of injection will be recorded. If injection site reactions are observed, mitigation procedures should be put in place as per local standard of care. Examples of mitigations include icing the injection site, rotating the quadrant of the abdomen in which the injection is administered, or providing antihistamine prior to injection.

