### 2.2 Study Design

#### 2.2.1 Overview

This is a Phase 2a, randomized, double-blind, placebo-controlled study evaluating the safety and efficacy of EFX in subjects with NASH.

Cohort C will enroll approximately 30 subjects with biopsy-proven NASH. All subjects in Cohort C will have F4 fibrosis. Subjects meeting the study's entry criteria will be randomly assigned in a 1:2 ratio into 2 treatment groups as shown in the figure below:

There will be no stratification for Cohort C. Study drug will be administered subcutaneously once weekly (QW) for a total of 16 weeks. After 16 weeks of treatment, a safety follow-up visit will occur at Week 20. Following 16 weeks of treatment, subjects will be given the option to collect an end of treatment biopsy.

This study will be conducted at approximately 30 sites in the U.S. Additional sites may be added, depending on subject accrual rates.

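### The SAP's sample code for FibroScan stiffness does not give a matched treatment effect estimate and 95% CI: the ESTIMATE line and the only printed interval for the difference run in opposite directions.

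*SAP*

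**What the plan says.** SAP section 3.4.1.1 analyses the Week 16 change and percent change in FibroScan stiffness by ANCOVA, with treatment as a factor and baseline stiffness as a covariate. On reporting it says: "The treatment effect estimate, 95% CI and pvalues will be provided". The sample code that follows has four relevant lines:

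- "class TREATMENT", with no REF= option and no ORDER= option on the PROC line;
- "model CHG = TREATMENT BASE / p", where `p` is the only option;
- "lsmeans TREATMENT / stderr pdiff cl";
- "estimate 'EFX 50 mg : Placebo' TREATMENT -1 1".

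The SAP does not give the stored values or the sort order of TREATMENT. The arm names in the code appear only in the ESTIMATE label. The protocol synopsis calls the Cohort C arms Group A (placebo) and Group B (50 mg EFX), and protocol section 5.2.2 lists placebo first, with 10 and 20 subjects. SAP section 3.1.5 sets the default test: "The statistical hypotheses will be tested at the 2-sided, 0.05 significance for the parameters with neutral direction unless specified otherwise". SAP section 7 names SAS 9.4 or higher and leaves the detailed programming to a separate document. Neither document says, for Cohort C, which arm is subtracted from which.

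**The concern.** A treatment effect estimate and its CI should describe the same difference. Here the labelled estimate comes from one statement and the only printed interval for the difference comes from another, and the two subtract in opposite orders. Nothing in the SAP tells the programmer which order is intended. For a change in stiffness, the sign says which arm improved more. Cohort C efficacy is not powered, so readers will lean on the estimate and interval more than on the p-value, and these are the two outputs that the sign affects.

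**Working it through.** The documents state no figure to reproduce, because this is a matter of contrast algebra.

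**Assumed SAS behaviour** (standard PROC GLM; not stated in the documents): CLASS levels sort by formatted value unless told otherwise; ESTIMATE coefficients apply to levels in that order; LSMEANS with PDIFF and CL reports limits for LS mean 1 minus LS mean 2; ESTIMATE prints limits only if CLPARM is on the MODEL statement.

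**Algebra.** Let m1 and m2 be the LS means of the first and second sorted levels.

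- ESTIMATE with -1 1: (-1) × m1 + (1) × m2 = m2 - m1.
- LSMEANS difference: m1 - m2 = -(m2 - m1).

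The two differ only in sign, whatever the levels are called. The variance of a contrast does not change when all its coefficients change sign, so the SE and the two-sided p-value are the same for both.

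**Which statement matches the label depends on the coding.** Both 'EFX 50 mg' and '50 mg EFX' sort before 'Placebo'. With either, level 1 is EFX and the labelled line gives placebo minus EFX. With Group A/Group B, or 0/1 with placebo as 0, level 1 is placebo and the labelled line gives EFX minus placebo.

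**Illustration.** The SAP's model was fitted by least squares to one invented data set with the planned arm sizes (10 placebo, 20 EFX; 30 - 3 = 27 residual df). It has a mean change of -1 on placebo and -5 on EFX at baseline 20, residual SD 4, baseline mean 20 and SD 5, and slope -0.2. SAS itself was not run, so this shows the consequence of the rules above and does not test them.

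| Sorted levels | ESTIMATE -1 1 | LSMEANS difference | LSMEANS 95% CI |
|---|---|---|---|
| EFX 50 mg, Placebo | +5.864 | -5.864 | (-8.839, -2.890) |
| 50 mg EFX, Placebo | +5.864 | -5.864 | (-8.839, -2.890) |
| Group A, Group B | -5.864 | +5.864 | (2.890, 8.839) |
| 0, 1 (placebo = 0) | -5.864 | +5.864 | (2.890, 8.839) |

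In all four rows the SE is 1.450 and p = 0.00039. With coefficients 1 -1 and EFX first, ESTIMATE gives -5.864, which lies inside (-8.839, -2.890).

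**When the mismatch shows itself.** Write d for the ESTIMATE value. The LSMEANS interval is -d ± t × SE, so d lies outside it only if 2|d| > t × SE, that is |d|/SE > t/2. Here t = (8.839 - 5.864)/1.450 = 2.052, so the threshold is about 1.03. For a smaller ratio the estimate falls inside the mirror-image interval and the table looks normal.

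**The case against.** Much of the case on the other side stands.

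- **The label may be right.** A reader might infer that the labelled line certainly computes placebo minus EFX. The documents do not support that. The SAP never says that TREATMENT is stored under the names in the label, and the documents' own order puts placebo first: Group A and Group B, the dosing list, and "randomly assigned in a 1:2 ratio into 2 treatment groups", which fits 10 and 20 only with placebo first.
- **Neither output need be wrong.** It is also tempting to say that one output has the wrong sign whatever the coding. A PDIFF difference is correct for its own direction; it is the same comparison in mirror image. Harm arises only when differently directed outputs are put in one row or the direction is misread.
- **The interval can be obtained another way.** The ESTIMATE value ± t × SE gives a matching interval by hand. CLPARM only prints it.
- **This is sample code.** Options may have been left off the PROC line, and section 7 leaves detailed programming to another document.
- **The reach is limited.** SAP section 3.4.1.2 asks for LS means, intervals and p-values for ELF and Pro-C3 and does not call for this contrast. Other Cohort C ANCOVAs share the model form, but nothing says they reuse this code.
- **There are safeguards.** The arms' LS means and the required summary statistics show the direction independently.

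One safeguard is weaker than it looks. An estimate outside its interval gives itself away, but that does not happen when the estimate is less than about 1.03 standard errors from zero. None of these points makes the code, followed as written, produce a matched estimate and CI.

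**Conclusion.** The point holds as a specification gap. Under standard PROC GLM rules, the code prints an estimate without an interval and an interval in the opposite direction, whatever the coding. Whether the label itself is wrong depends on a level order that the SAP does not fix. The size is modest: SEs, two-sided p-values and LS means are unaffected, the endpoint is secondary and unpowered, and Cohort C's primary objective is safety. The exposure is a misreported sign, or an estimate beside a mirror-image interval. The documents do not support a claim that the stiffness result will be reversed, or that ELF and Pro-C3 inherit the problem. The conclusion assumes the SAS defaults listed in the working and a programmer who follows the sample code literally.

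**What to change.** In section 3.4.1.1:

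1. Set the TREATMENT level order explicitly, for example with placebo stored as 0, EFX as 1, and `order=internal` on the PROC line.
2. Make the ESTIMATE coefficients give EFX minus placebo under that order: -1 1 if placebo is first, 1 -1 if EFX is first. Word the label as EFX minus placebo.
3. Add `clparm` to the MODEL options, and take both the reported estimate and its 95% CI from ESTIMATE. Keep LSMEANS for the arm means and drop its difference from the reported output.
4. Add one sentence: differences are EFX minus placebo, and for stiffness a negative value means a larger reduction on EFX.

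Carry the same convention into the programming specifications. The cost is a few words of code and one sentence; no data, sample size or test changes.
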